1.1. Synopsis

Protocol Title: An Open-Label, Randomized Study to Evaluate the Relative Bioavailability of Selpercatinib in 3 Formulations for Pediatric Use

Brief Title: A Relative Bioavailability Study of Selpercatinib Formulations for Pediatric Use

Rationale:

This is a bioavailability testing the different formulation that has been used in pediatric studies

Objectives, Endpoints, and Estimands:

Objectives	Endpoints
Primary	

 To evaluate the relative bioavailability of RTU and PFOS suspensions compared to the capsule formulation 	
 C_{max}, $AUC(0-\infty)$, $AUC0-t_{last}$, and t_{max} of selpercatinib
Secondary	
 To evaluate the safety and tolerability of a single dose of 20-mg oral dose of selpercatinib RTU and PFOS suspensions To assess the palatability of selpercatinib RTU and PFOS suspensions

Overall Design:

Study JZJU will be an open-label, Phase 1 randomized, 3-formulation, 3-period, crossover study in adult healthy male and female participants. The ready-to-use (RTU) 20 mg suspension and the powder for oral suspension (PFOS) 20 mg/mL suspension will be compared to the 20 mg capsule formulation

Safety assessments, including AEs, concomitant medications, medical assessments, clinical laboratory tests, vital signs, and ECGs, and blood sampling for PK, will be performed.

[figure not shown]
Screening

All participants will be screened within 28 days prior to enrollment.

Treatment and Assessment Period

Participants will be admitted to the CRU on Day -1. On the morning of Day 1, participants will be randomized to 1 of 3 treatment sequences and will receive single doses of 20-mg selpercatinib on each of Days 1, 8, and 15 as either the RTU suspension, the PFOS, or the capsule, and will be dosed according to the randomization sequence following an overnight fast of at least 10 hours.

The treatment sequences to be used are as follows:

Abbreviations: PFOS = powder for oral suspension; RTU = ready to use.

There will be a washout of 7 days between doses of selpercatinib.

Participants will remain resident at the CRU for the full duration of the treatment period (i.e., up to Day 21).

Number of Participants:

Up to approximately 42 participants will be enrolled to ensure that at least approximately 36 participants complete the study.

[figure not shown]
Intervention Groups and Duration:

Participants will participate in 1 treatment.

The study duration for all participants is expected to be up to 59 days.

Data Monitoring Committee: No

1.2. Schema

★ 20 mg selpercatinib as either the RTU suspension, the PFOS, or the capsule, according to the randomization schedule

▼ admission to the CRU

▼ discharge from the CRU / study discharge

Abbreviations: CRU = clinical research unit; PFOS = powder for oral suspension; RTU = ready to use.

1.3. Schedule of Activities (SoA)

Procedure	Screening	Days																					ED	Comments	
		-28 to -2 days prior to Day 1	1	2	3	4	5	6	7	8	9	10	11	12	13	14	15	16	17	18	19	20	21		
Informed consent	X																								
Inclusion and exclusion criteria	X																								
Demography	X																								
Participant Admission to CRU		X																							
Participant Discharge from CRU																							X		
Outpatient visit	X																								
Medical history (includes substance usage [and family history of premature cardiovascular disease])		X																							
Past and current medical conditions		X																							
Physical examination	X	X																				X	X	Full physical examination (including height and weight) to be performed at	

Procedure	Screening	Days																					ED	Comments		
		-1	1	2	3	4	5	6	7	8	9	10	11	12	13	14	15	16	17	18	19	20	21			
	-28 to -2 days prior to Day 1																									
Serum or urine pregnancy test (all females)		X	X																							screening. Symptom-driven physical examinations to be performed at all other timepoints.
HIV, and hepatitis B and C screen		X																								Serum pregnancy test will be performed at screening. Urine pregnancy test will be performed at admission to the CRU.
Urine or breath ethanol test		X	X																							
Urine drug screen		X	X																							
12-lead ECG		X		P, 2h						P, 2h						P, 2h					X	X			Single ECGs are required.	
Vital signs (supine)		X	X	P, 1, 2h	24 h			X		P, 1, 2h	24 h			X		P, 1, 2h	24 h			X	X	X			Time points may be added, if warranted and agreed upon between	

Procedure	Screening	Days																					ED	Comments	
		1	1	2	3	4	5	6	7	8	9	10	11	12	13	14	15	16	17	18	19	20	21		
	-28 to -2 days prior to Day 1																								Lilly and the investigator. Assessments on Days 5 12, and 19 should be performed in the morning at a time relative to predose on Days 1, 8 and 15, respectively.
Clinical laboratory tests (include liver chemistries)	X	X		24 h					X	24 h					X		24 h					X	X	See Appendix 2 (Section 10.2), Clinical Laboratory Tests, for details.	
Genetic sample			X																						

CCI

	Screening	Days																					ED	Comments	
Procedure	-28 to -2 days prior to Day 1	1	1	2	3	4	5	6	7	8	9	10	11	12	13	14	15	16	17	18	19	20	21		
		CCI																							
Randomization			X																						
Selpercatinib administration			X							X								X							
Taste Assessment Questionnaire				X							X							X							To be performed for the RTU suspension and PFOS formulations only immediately after dosing.
Adverse event /Serious adverse event review	X	X	←————→																		X				
Concomitant medication review	X	X	←————→																		X				

Abbreviations: CRU = clinical research unit; ECG = electrocardiogram; ED = early discontinuation; HIV = human immunodeficiency virus; P = predose; PFOS = powder for oral suspension; PK = pharmacokinetic; RTU = ready to use.

2. Introduction

Selpercatinib (LY3527723) has been developed by Loxo Oncology, Inc and acquired by Eli Lilly and Company (Lilly), and has been approved by the Food and Drug Administration for the treatment of advanced or metastatic RET-mutant MTC; advanced or metastatic RET fusion-positive thyroid cancer, in adults and children ≥ 12 years; and for the treatment of metastatic RET fusion-positive non-small cell lung carcinoma (NSCLC) in adults. Full details of the preclinical and clinical safety and tolerability data are contained in the investigator's brochure (IB).

2.1. Study Rationale

This is a relative bioavailability study testing the different formulations that has been used in pediatric studies.

2.2. Background

Selpercatinib (LY3527723) is a highly potent and specific small-molecule inhibitor of the RET kinase, with minimal inhibition of other kinase and nonkinase targets.

Selpercatinib doses have been evaluated in healthy participants and patients with advanced or metastatic RET-mutant MTC, advanced or metastatic RET fusion-positive thyroid cancer, other RET fusion-positive solid tumors, and metastatic RET fusion-positive NSCLC across Phase 1, 2, and 3 clinical studies. Across these studies, single oral doses of selpercatinib were administered over a range of 20 to 720 mg. Multiple oral doses of 160 mg/day selpercatinib were administered orally twice daily for 10 days in healthy volunteers. Pediatric dose was selected to be 92 mg/m^2 , (maximum 160 mg BID).

The pharmacokinetics of selpercatinib is characterized by good oral bioavailability, with a t_{max} of approximately 2 hours (range 0 to 8.1 hours). CYP3A4 mediated metabolism constitutes the major route of elimination, and the $t_{\frac{1}{2}}$ is approximately 32 hours in healthy volunteers. The $V_{\text{ss/F}}$ and CL/F of selpercatinib increased with increasing body weight (27 kg to 177 kg). No clinically significant differences in the PK of selpercatinib were observed based on age (15 years to 90 years), or sex. As the PK of selpercatinib have been demonstrated to be linear in the dose range of 20 to 160 mg in adult cancer patients, results from study JZJU can be expected to be applicable across the therapeutic dose range.

More detailed information about the pharmacokinetics (PK) and absorption, distribution, metabolism, and excretion properties of selpercatinib may be found in the IB.

2.3. Benefit/Risk Assessment

There is no anticipated therapeutic benefit for the healthy participants in this study. However, participants may benefit from the screening procedures (through detection of unknown health issues) even if they receive no therapeutic benefit from the study.

The dose of selpercatinib to be given in this study is 20 mg. The safety profile of selpercatinib is very well tolerated in healthy volunteers, with the low rates of study drug discontinuation due to adverse events (AEs).

As outlined in the IB, the most common toxicities associated with selpercatinib in patients are monitorable and reversible and include dry mouth, diarrhea, hypertension, fatigue, constipation, AST/ALT elevation, headache, nausea, edema peripheral, abdominal pain, rash, electrocardiogram (ECG) QT prolonged, cough, vomiting, dyspnea and increased blood creatinine. Events of special interest include hypersensitivity, liver-function test abnormalities, thrombocytopenia, and hypertension. None of these events of special interest have been observed to date in healthy participants.

More detailed information about the known and expected benefits and risks and reasonably expected AEs of selpercatinib may be found in the IB.

3. Objectives and Endpoints

Objectives	Endpoints
Primary	

 To evaluate the relative bioavailability of RTU and PFOS suspensions compared to the capsule formulation 	
 C_{max}, $AUC(0-\infty)$, $AUC0-t_{last}$, and t_{max} of selpercatinib
Secondary	
 To evaluate the safety and tolerability of a single 20-mg oral dose of selpercatinib RTU and PFOS suspensions To assess the palatability of selpercatinib RTU and PFOS suspensions
	
 Summary of the number, severity, and type of treatment-emergent AEs and serious adverse events Responses to palatability questionnaire (RTU suspension only)

Abbreviations: AE = adverse event; $AUC(0-\infty)$ = area under the concentration versus time curve from time zero to infinity; $AUC0-t_{last}$ = area under the concentration versus time curve from time zero to time t , where t is the last time point with a measurable concentration; C_{max} = maximum observed drug concentration; PFOS = powder for oral suspension; RTU = ready to use; t_{max} = time to maximum observed drug concentration.

4. Study Design

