8.10. Product Acceptability and Palatability Assessments

The participant will be asked to provide responses to questions designed to assess the acceptability and palatability of the RTU suspension. The questionnaire will assess the participant's experience relating to the taste, smell, and after taste in the oral cavity.

The questionnaire will be completed by the participant immediately after administration of the RTU suspension and PFOS formulations.

9. Statistical Considerations

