#### **9.4.7 Palatability Questionnaires**

The participant will be asked to provide responses to questions designed to assess the acceptability and palatability of the RTU suspension. The questionnaire will assess the participant's experience relating to the taste, smell, and after taste in the oral cavity.

The questionnaire will be completed by the participant immediately after administration of the RTU suspension and PFOS formulations.

These data will be summarized by treatment, and listed.

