### **11. CHANGES FROM THE PROTOCOL SPECIFIED STATISTICAL ANALYSES**

There were no changes from the protocol specified statistical analyses.

---

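### Does the RTU-only wording of the palatability endpoint leave the PFOS suspension without a palatability result?

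*Protocol*

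**What the plan says.** Protocol Section 3 sets a secondary objective, "To assess the palatability of selpercatinib RTU and PFOS suspensions", and SAP Section 4 repeats it. The endpoint listed against it in both documents is "Responses to palatability questionnaire (RTU suspension only".

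The collection instructions cover both liquids. The comment on the taste questionnaire row of the Schedule of Activities (Protocol Section 1.3) reads "To be performed for the RTU suspension and PFOS formulations only immediately after dosing".

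Protocol Section 8.10 and SAP Section 9.4.7 are each mixed. Each opens by describing questions "designed to assess the acceptability and palatability of the RTU suspension", and each then says "The questionnaire will be completed by the participant immediately after administration of the RTU suspension and PFOS formulations". SAP Section 9.4.7 closes with the analysis instruction, "These data will be summarized by treatment, and listed". SAP Section 11 adds "There were no changes from the protocol specified statistical analyses".

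**The concern.** In the objectives table an objective that names two products is paired with an endpoint that names one, and the word only makes this look like a deliberate exclusion. The same words stand in both documents, and the opening sentences of Protocol Section 8.10 and SAP Section 9.4.7 lean the same way. SAP Section 11 declares no departures, so nothing there explains the mismatch.

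The study is about formulations for children, and palatability is one of its two secondary objectives. If the endpoint governed reporting, the PFOS responses could be left out, or called additional, after the results of an open-label, subjective measure had been seen. A related worry is that each completer rates both suspensions, yet the SAP promises only a summary by treatment and no within-participant contrast.

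**Working it through.** The plan states no figure to reproduce on this point. The check is which formulations each element of the plan covers.

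| Element | Place | Covers |
|---|---|---|
| Objective | Protocol 3, SAP 4 | RTU and PFOS |
| Endpoint | Protocol 3, SAP 4 | RTU only |
| Collection | Schedule of Activities | RTU and PFOS |
| Purpose sentence | Protocol 8.10, SAP 9.4.7 | RTU only |
| Completion sentence | Protocol 8.10, SAP 9.4.7 | RTU and PFOS |
| Analysis | SAP 9.4.7 | by treatment, no restriction |

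**Which text governs the output?** Protocol Section 9 specifies no palatability analysis. SAP Section 3 says the SAP supersedes the protocol's statistical considerations. SAP Section 9.1 limits summaries to data for which the SAP details them, and SAP Section 9.4.7 does so here. It is therefore the operative instruction.

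**What does it cover?** The instruction directly follows the sentence naming both suspensions, so the data it refers to are the RTU and PFOS responses. SAP Section 6 lists three treatments for the outputs: capsule, RTU and PFOS. The capsule is not rated, so a summary by treatment has two columns, RTU and PFOS. Under an RTU-only reading there would be one column, and the phrase would have little meaning. SAP Section 9.1 also requires listings of everything in the database.

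**How many responses are affected?** Inputs are from Protocol Section 9.5: about 36 completers, up to about 42 enrolled.

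- Questionnaires: 2 × 36 = 72 to 2 × 42 = 84. The upper figure assumes that everyone enrolled takes both suspensions.
- PFOS share: one half, so 72 / 2 = 36 to 84 / 2 = 42.
- PFOS responses left out of the SAP Section 9.4.7 summary: 0.

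The 36 to 42 responses lie outside the wording of the endpoint, but they are collected, summarised and listed.

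**What would deleting the parenthesis change?** The questionnaire schedule, the summary by treatment and the listing would all be the same. So would the sample size, which rests on the precision of the geometric mean ratios for Cmax and AUC.

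**Is a paired RTU–PFOS summary missing?** The objective asks for each suspension's palatability to be assessed; the only comparison among the objectives is of bioavailability with the capsule. The documents give the topics (taste, smell, aftertaste) but not the items or response scale. If the answers are categories without numerical scores, an RTU-minus-PFOS difference is not defined. SAP Section 9.1 already provides summaries for either data type: counts and percentages, or means, SDs and medians.

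**The case for a change.** The strongest case for a change is that a pre-specified plan should not leave the status of half the questionnaires to interpretation. The SAP was written after review of the amended protocol and is meant to serve as the template for the study report, yet it repeats the restriction. One analyst could report the PFOS ratings under the secondary endpoint and another could present them as additional, each with some textual support. Reconciling the wording would cost a few words and no new data.

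The inconsistency itself stands: the endpoint and the two purpose sentences disagree with the objective, the Schedule of Activities and the completion sentences. The feared consequence does not. Leaving PFOS out of the table would depart from SAP Section 9.4.7, so it is not a free choice once the data are in. What remains open is the label on the PFOS column, and SAP Section 9.4.9 plans no inferential analysis for this group of assessments, so no test or error rate depends on that label.

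The case for a paired summary is weaker. It fits a crossover, but Protocol Section 4.2 invokes own-control comparisons for safety and pharmacokinetics, not for taste. The listings keep each participant's two sets of responses, and SAP Section 3 allows supplementary analyses if they are identified in the study report.

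**Conclusion.** No change to the plan follows. The endpoint wording is a clerical slip in a descriptive secondary endpoint. PFOS palatability is collected under the Schedule of Activities and Protocol Section 8.10, then summarised and listed under SAP Section 9.4.7, so the PFOS half of the objective is answered. No responses are lost, and the pharmacokinetic analysis and sample size are unaffected. The other secondary objective, safety and tolerability, has an endpoint with no RTU restriction, so the slip is confined to palatability. The lack of a paired contrast is a matter of preference, since the objective does not ask for one.

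This rests on reading the analysis instruction in SAP Section 9.4.7 as covering both suspensions named in the sentence before it. The separate table shells and the questionnaire items are not in the documents, so the exact layout cannot be confirmed. The synopsis endpoints for the secondary objectives are not legible in the available text, and nothing is inferred from them. If RTU alone was intended, the PFOS column is surplus and the RTU result is the same. The wording can be tidied if either document is reopened for another reason.

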4.1. Overall Design

Study JZJU will be an open-label, Phase 1 randomized, 3-formulation, 3-period, crossover study in adult healthy male and female participants. The ready-to-use (RTU) 20-mg suspension and the powder for oral suspension (PFOS) 20 mg/mL formulation will be compared to the 20 mg capsule formulation.

The schematic in Section 1.2 illustrates the study design.

Safety assessments, including AEs, concomitant medications, medical assessments, clinical laboratory tests, vital signs, and ECGs, and blood sampling for PK, will be performed according to the SoA (Section 1.3).

[figure not shown]
4.1.1. Screening

All participants will be screened within 28 days prior to enrollment.

4.1.2. Treatment and Assessment Period

Participants will be admitted to the clinical research unit (CRU) on Day -1. On the morning of Day 1, participants will be randomized to 1 of 3 treatment sequences and will receive single doses of 20 mg selpercatinib on each of Days 1, 8, and 15 as either the RTU suspension, the PFOS, or the capsule, and will be dosed according to the randomization sequence following an overnight fast of at least 10 hours.

The treatment sequences to be used are as follows:

Abbreviations: PFOS = powder for oral suspension; RTU = ready to use.

There will be a washout of 7 days between doses of selpercatinib.

Participants will remain resident at the CRU for the full duration of the treatment period (i.e., up to Day 21).

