9.5. Sample Size Determination

Up to approximately 42 participants will be enrolled to ensure that at least approximately 36 participants complete the study. The sample size for this study is justified based on a precision for the ratio of geometric means and it is represented by the half-width of the 90% CI of the point estimate on the logarithmic scale. Based on an intra-subject variability of 70% (LOXO-RET-19075), with a probability of 90%, a 90% CI for the ratio of the geometric means for C_{max} and AUC will be obtained with a precision about 0.288 in the log scale, which corresponds to approximately 0.334 in the natural scale.

10. Supporting Documentation and Operational Considerations

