### **Treatment of Outliers during Pharmacokinetic Analysis**

Application of this procedure to all PK analyses is not a requirement. Rather, this procedure provides justification for exclusion of data when scientifically appropriate. This procedure describes the methodology for identifying an individual value as an outlier for potential exclusion, but does not require that the value be excluded from analysis. The following methodology will not be used to exclude complete profiles from analysis.

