#### Data within an Individual Profile

A value within an individual profile may be excluded from analysis if any of the following criteria are met:

- For PK profiles during multiple dosing, the concentration of the pre-dose sample exceeds all measured concentrations for that individual in the subsequent post-dose samples.
- For PK profiles during single dosing of non-endogenous compounds, the concentration in a pre-dose sample is quantifiable.
- For any questionable datum that does not satisfy the above criteria, the profile will be evaluated and results reported with and without the suspected datum.

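### Should three treatment sequences be replaced by all six, with an added carryover analysis, because three cannot balance carryover among three formulations?

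*Protocol*

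**What the plan says.** Protocol 4.1.2 and SAP 5.2 describe a three-formulation, three-period crossover in which "participants will be randomized to 1 of 3 treatment sequences". The sequences are listed in a figure that is not shown. Protocol 4.1.2 adds: "There will be a washout of 7 days between doses of selpercatinib". Protocol 2.2 says the half-life "is approximately 32 hours in healthy volunteers".

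SAP 9.3.2 fits formulation, period and sequence as fixed effects and participant as a random effect. The visible text has no carryover term. Some lines after the model are redacted.

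Protocol 9.5 gives a 90% CI half-width of about 0.288 on the log scale, "which corresponds to approximately 0.334 in the natural scale".

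Under its outlier procedure in 9.3.1, the SAP lists one condition that permits dropping a single value: "For PK profiles during single dosing of non-endogenous compounds, the concentration in a pre-dose sample is quantifiable". The procedure is permissive; it "does not require that the value be excluded from analysis". It also states: "The following methodology will not be used to exclude complete profiles from analysis". For questionable values that meet none of the listed conditions, "the profile will be evaluated and results reported with and without the suspected datum".

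**The concern.** Three formulations form six ordered pairs. In a three-sequence Latin square each formulation always follows the same other one, so any residual drug falls unevenly on the comparisons. The planned model has no term to separate it. If the formulations differ in exposure, the ratio of a suspension to the capsule is biased, in a direction set by which three sequences were chosen.

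The predose rule appears to make this worse. A quantifiable predose value in Period 2 or 3 may be residual drug from the previous formulation. The SAP allows that point to be dropped, while the residual stays in the postdose concentrations and so in Cmax and AUC. The with-and-without reporting does not cover it, because it meets a listed condition. The visible text gives no predose summary by period and no carryover sensitivity analysis.

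The remedy also looks free: the 42 enrolled and 36 completers both divide by six, and no participants, visits or samples are added.

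**Working it through.** **Inputs.** Washout 168 h (Protocol 4.1.2); half-life about 32 h (Protocol 2.2); N = 36 completers, intra-participant CV 70%, 90% CI, 90% probability (Protocol 9.5).

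**The plan's own figure.** σ = √ln(1 + 0.70²) = 0.631. Half-width = t(0.95, df) × σ × √(2/36) × √(χ²(0.90, df)/df). With df = 35 this is 0.2885, against the stated 0.288, and exp(0.288) − 1 = 0.334. The figure reproduces.

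**Balance.** There are 20 ways to choose three of the six sequences. None covers all six ordered pairs. Two are Latin squares, covering three pairs each; the other 18 cover five. All six sequences cover every pair twice. This holds whatever the missing figure shows.

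**Precision of the planned model.** The contrast variance is 2.0 × σ²/N for either Latin square and also for six sequences. The expected half-width at N = 36 (68 df) is 0.248 in both cases.

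**Residual.** 168/32 = 5.25 half-lives and 2^(−5.25) = 0.0263. The residual reaches 5% at 168/log₂(20) = 38.9 h.

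**Bias.** Assume mono-exponential decline, with capsule = 1 and d = 0.0263. Observed log exposure is then log(F + d·F_prev + d²·F_prev2), where F is the formulation's own exposure and the other terms come from the one or two doses before. Call capsule–RTU–PFOS and its cyclic shifts square A, and capsule–PFOS–RTU and its shifts square B. Example for square A with true ratios RTU 0.8, PFOS 1.25:

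- PFOS follows RTU. Its log excess is 0 in Period 1, ln(1 + 0.0263 × 0.8/1.25) = 0.0167 in Period 2 and 0.0172 in Period 3; mean 0.0113.
- The capsule follows PFOS. Its log excess is 0, ln(1 + 0.0263 × 1.25) = 0.0323 and 0.0329; mean 0.0217.
- Bias of PFOS/capsule = 0.0113 − 0.0217 = −0.0104, or −1.0%.

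The same calculation for other cases (bias in the RTU ratio / PFOS ratio):

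| Half-life, true ratios | Square A | Square B | Six sequences |
|---|---|---|---|
| 32 h, 1.0 / 1.0 | 0 / 0 | 0 / 0 | 0 / 0 |
| 32 h, 0.9 / 1.1 | +0.0 / −0.5% | +0.6 / +0.0% | +0.3 / −0.2% |
| 32 h, 0.8 / 1.25 | +0.0 / −1.0% | +1.3 / −0.0% | +0.7 / −0.5% |
| 32 h, 1.0 / 0.6 | +0.7 / +1.9% | −0.7 / +1.2% | 0.0 / +1.5% |
| 48 h (assumed), 0.6 / 1.4 | +1.8 / −5.1% | +9.5 / +0.4% | +5.6 / −2.4% |

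Six sequences roughly average the two squares. For some contrasts one square does better. In an extreme case at 32 h, with one suspension at 0.5 and the other at 2.0, the largest log bias is 0.058 with a square and 0.029 with six sequences.

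**A carryover-adjusted model.** Its contrast variance is 10.0 × σ²/N for a Latin square and 2.5 for six sequences, so half-widths are 0.555 and 0.278 (66 df). Only six sequences make the model usable. However, residual drug adds to exposure on the natural scale, and its log effect depends on both the current and the previous formulation. A simple first-order term on the log scale does not match that. With six sequences at 32 h, the PFOS bias at 1.0/0.6 goes from +1.5% to +1.1%, and at 0.8/1.25 the pair goes from +0.7/−0.5% to +0.5/−0.3%. The half-width meanwhile grows by 0.278 − 0.248 = 0.030.

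**Omitting participant-periods with predose above 5% of that period's Cmax.** The denominator is the outcome, so periods with low Cmax are dropped preferentially. Simulated with 32 h in everyone, CV 70% and six sequences, about 22% of Period 2 and 3 profiles are dropped even when the formulations are equal. At true ratios 1.0/0.6, about 42% of PFOS profiles go against 16% of capsule profiles, and the PFOS bias rises from about +2% to about +17%.

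**The case for a change.** The strongest case for acting is that the change costs almost nothing before dosing starts, while the assumption of negligible carryover is left untested. The half-life is only approximate, participants with more than 38.9 h carry over more than 5%, and the SAP allows the one direct sign of carryover, a quantifiable predose value, to be dropped without a sensitivity result.

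Part of this stands. The counting argument is exact, six sequences lose no precision in the planned model compared with a Latin square, and a descriptive summary of Period 2 and 3 predose values would do no harm. A team whose randomization list is still open could reasonably prefer six.

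The claim of a material gain does not stand. The largest bias in the table, 9.5%, needs a 48 h half-life in every participant, which the documents do not support, together with suspensions at 0.6 and 1.4 of the capsule. Neither added analysis provides a sound check: one leaves most of the bias in place and the other creates more.

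Nor is the predose information lost. SAP 9.1 lists all databased data, and the section on reporting excluded values requires exclusions to be documented in the study report. Dropping a predose point is optional, so an analyst can compare it with Cmax from the listing. Whether a summary is already planned cannot be judged, because lines of SAP 9.3.2 are redacted and the table shells named in SAP 3 are a separate document.

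**Conclusion.** No change follows. Three sequences leave first-order carryover unbalanced, but with 5.25 half-lives of washout the bias is zero for equal exposures, at most about 1.3% for true ratios within 0.8 to 1.25, and about 1.9% at 1.0/0.6. Even the extreme 0.5/2.0 case gives 0.058 on the log scale, against a planned half-width of 0.288. Six sequences would about halve the worst case without removing it. Three sequences with this washout are a fair design choice, and the missing predose summary is a detail that analysts can fill from the listings.

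This rests on a half-life near 32 h, mono-exponential decline and proportional superposition. The bias figures also assume that the three sequences form a Latin square, which the missing figure prevents us from confirming.
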